3.4.2. Handling of Values Below or Above a Threshold

Values below (above) the detection limit will be imputed by the value one unit smaller (larger) than the detection limit itself. In listings, the original value will be presented.

Example: if the database contains the value “<0.04”, then for the descriptive statistics the value “0.03” will be used. The value “>1000” will be imputed by “1001”.

3.4.3. Handling of Outliers

There will be no outlier detection, all measured values will be included in the analyses.

In the PK part of the analysis, exclusion of abnormal PK concentration results will be formally discussed and determined after data base lock and before running the final statistical analysis in the PK Data Review Report.

3.4.4. Stratification Factors

The analyses will be stratified by the type of IPF SOC medication taken at randomization: nintedanib or pirfenidone or neither. In all analyses, except if indicated otherwise, the stratum will be the SOC at randomization and will not change if the subject switches SOC during the study.

The 3 strata could differ in their safety profile, in addition, they might have different effects on the biomarker results (depending on the biomarker) and efficacy results. Therefore, for all analyses, 3 strata will be used (nintedanib, pirfenidone, neither), unless indicated otherwise.

The stratum reported in the case report form (CRF) will be used in the analyses. Any discrepancies in stratification reported in the interactive web response system (IWRS) versus CRF will be listed.

3.5. Presentation of Results

3.5.1. Presentation of Treatment Groups

Results will be presented by treatment group:

- GLPG1205 100 mg
- Placebo

In the section Subject Information, a grand total “All Subjects” will be added to summarize all subjects over all treatment groups in tables and figures.

3.5.2. Calculation of Descriptive Statistics

Descriptive statistics will include:

- the number of non-missing data points (N)
- the arithmetic mean
- the standard error (SE) and standard deviation (SD)
- the median, minimum and maximum
- 95% confidence interval (CI) of the mean (if indicated in the relevant section).

3.5.3. Calculation of Percentages

Frequencies and percentages will be generated for categorical parameters.

For event-type data (e.g. adverse events), the denominator will be all subjects in the analysis set and analysis period. For other data (e.g. worst-case analysis of assessments), the denominator will be all subjects with (post-baseline) data for the parameter, in the analysis set and analysis window/period.

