7.3.4.2. Secondary Efficacy Endpoints Analyses

The % predicted FVC change from baseline will be analyzed using a similar model as the one described for the primary analysis.

The proportions of subjects who have an absolute decline of 10 percentage points or more in % predicted FVC or who die will be analyzed using logistic regression.

Treatment effect on time to death (all cause and respiratory-related) / hospitalization (all cause and respiratory-related), whichever occurs first, will be assessed using the log-rank test. Kaplan-Meier estimates will be derived for probability of death (all cause and respiratory-related) / hospitalization (all cause and respiratory-related) (whichever occurs first) over time and displayed graphically.

SGRQ total score and domains will be analyzed using descriptive statistics of actual values and changes from baseline at all time points. The proportion of SGRQ responders (defined as absolute change from baseline at all time points, in SGRQ total score \leq -4 points) will also be tabulated.

SGRQ responders and proportion of subjects with hospitalization will be described and tested for treatment differences using a Fisher's exact test.

More detail will be provided in the SAP.

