2.2.2. Secondary Endpoints

- Safety and tolerability changes over time (baseline to 26 weeks).
- Time to any of major events (whichever occurs first) defined as:
 - Death (all-cause and respiratory-related)
 - First hospitalization (all-cause and respiratory-related)
- Change from baseline 26 weeks in functional exercise capacity, assessed by the 6MWT at Week 26.
- Change from baseline until 26 weeks in quality of life measures, assessed by the St. George's Respiratory Questionnaire (SGRQ) total score and domains and proportion of SGRQ responders.
- Plasma concentrations of GLPG1205, nintedanib and pirfenidone.

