3.4.1.2. Handling of Missing Result Data

No imputation will be done of missing result data. That is, an observed cases (OC) analysis will be performed. Details on the sensitivity analyses to investigate the impact of missing data on efficacy parameters are described in Section 6.2.

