The proportion of SGRQ responders at Week 26 (defined as absolute change from baseline in SGRQ total score ≤ -4 %, at least once) will also be tabulated per treatment group. Treatment effect on SGRQ responders will be assessed using the Fisher's exact test.

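### The SGRQ responder proportion defaults to an observed-case rate, so subjects who die or discontinue without a qualifying score drop out of the comparison; who drops out depends on an unsettled responder time point

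*SAP*

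**What the plan says.** - **Endpoint.** SAP 2.2.2 lists, among the secondary endpoints, SGRQ "total score and domains and proportion of SGRQ responders".
- **Test.** SAP 5.2.3.3: "Treatment effect on SGRQ responders will be assessed using the Fisher's exact test". Protocol 7.3.4.2 plans the same test.
- **Definition.** SAP 5.2.3.3 opens with "The proportion of SGRQ responders at Week 26", then defines a responder as a total-score change of −4 or lower reached at least once. Protocol 7.3.4.2 refers instead to the change at all time points. These are three different time references.
- **Denominator.** SAP 5.2.3.3 states none. SAP 3.5.3 separates two cases. First: "For event-type data (e.g. adverse events), the denominator will be all subjects in the analysis set and analysis period". For everything else, "the denominator will be all subjects with (post-baseline) data for the parameter, in the analysis set and analysis window/period".
- **Missing data.** SAP 3.4.1.2: "No imputation will be done of missing result data. That is, an observed cases (OC) analysis will be performed". It refers to a Section 6.2 for sensitivity analyses, but SAP Section 6 is the reference list. The analyses that exist, in SAP 5.2.2.2, are sensitivity analyses to the primary (FVC) analysis. The optional multiple imputation in Protocol 7.3.4.1 also concerns only the primary analysis.

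No visible text counts a subject without an SGRQ score as a non-responder.

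**The concern.** A responder rate among subjects who have a score is a rate among those who survived and stayed long enough to give one. Death and discontinuation happen after randomisation and may depend on treatment, so removing these subjects means that the groups compared are no longer the randomised groups.

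The design makes such loss likely. Under Protocol 4.2, a subject who stops IMP early is asked to attend EOT and follow-up but is not obliged to. The schedule has SGRQ at baseline, Week 12, Week 26 and EOT, and none at Visit 10. Under SAP 3.3.3 assessments are windowed by study day, so an EOT questionnaire before Day 163 is not a Week 26 value.

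At stake is one secondary estimate and its Fisher test. The estimate is also in the optional interim output for planning later studies (SAP 4.2). With about 20 placebo subjects, each one removed moves the rate visibly.

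**Working it through.** **1. The plan's own figure.** The only design figures are in Protocol 7.1 and concern FVC; there is none for SGRQ response. Inputs: 40 and 20 subjects, SD 200 mL, true differences of 50 and 80 mL in equal halves, 10% dropout.
- Mean difference = 0.5 × 50 + 0.5 × 80 = 65 mL.
- SE with 36 and 18 subjects = 200 × √(1/36 + 1/18) = 57.74 mL.
- P(observed > 40 mL) = 1 − Φ((40 − 65)/57.74) = 66.7%; P(observed > 20 mL) = 1 − Φ((20 − 65)/57.74) = 78.2%.

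The stated 67% and 78% reproduce. What carries over is the arm sizes and the 10% overall dropout, the only loss figure in the documents.

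**2. Who is removed.**
- *If the Week 26 wording governs:* everyone without a score in the Week 26 window (Days 163 to 197) is removed. That covers deaths and early discontinuations. It also covers incomplete questionnaires that yield no total score, missed questionnaires, and Visit 9 assessments that the COVID-19 extension moves past Day 197 into the Week 30 window.
- *If the at-least-once wording governs:* only subjects with no post-baseline SGRQ are removed. A subject who responded at Week 12 and then died counts as a responder.

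**3. Inflation of each arm's rate.** With r responders, n subjects and m missing, the observed-case rate is r/(n − m) and the non-responder rate is r/n. Their ratio is n/(n − m) = 1/(1 − missing share): 1.05 at 5%, 1.11 at 10%, 1.25 at 20%, 1.33 at 25%.

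**4. Effect on the difference.** Responder counts and missing splits below are assumed (GLPG1205 of 40; placebo of 20).

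| Responders | Missing | Observed case | Difference (Fisher p) | Missing = non-response | Difference (Fisher p) |
|---|---|---|---|---|---|
| 12; 6 | 4; 2 | 12/36 = 33.3%; 6/18 = 33.3% | 0 (1.00) | 30%; 30% | 0 (1.00) |
| 12; 6 | 8; 1 | 12/32 = 37.5%; 6/19 = 31.6% | +5.9 (0.77) | 30%; 30% | 0 (1.00) |
| 12; 6 | 10; 0 | 12/30 = 40%; 6/20 = 30% | +10 (0.56) | 30%; 30% | 0 (1.00) |
| 12; 6 | 0; 5 | 12/40 = 30%; 6/15 = 40% | −10 (0.53) | 30%; 30% | 0 (1.00) |
| 14; 5 | 4; 2 | 14/36 = 38.9%; 5/18 = 27.8% | +11.1 (0.55) | 35%; 25% | +10 (0.56) |
| 14; 5 | 4; 5 | 14/36 = 38.9%; 5/15 = 33.3% | +5.6 (0.76) | 35%; 25% | +10 (0.56) |

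Equal loss leaves a zero difference at zero and stretches a 10-point difference by about 1 point. Unequal loss favours the arm that lost more, whichever that is.

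**5. Range at the plan's 10% overall loss.** That is 6 of 60 subjects. With 12 and 6 responders:
- all 6 missing on GLPG1205: 12/34 − 6/20 = 35.3% − 30.0% = +5.3 points;
- all 6 missing on placebo: 12/40 − 6/14 = 30.0% − 42.9% = −12.9 points;
- against 0 with non-responder counting.

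**6. The same in rates.** If both arms have observed-case rate p, the two methods differ by p × (difference in missing shares). For 20% against 5% missing this is 3.0, 4.5 and 6.0 points at p = 20%, 30% and 40%.

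**The case against.** Observed cases is an explicit, prespecified choice, and non-responder counting is a different estimand rather than the only correct one. The study is a proof of concept without multiplicity adjustment, SGRQ scores are also analysed by ANCOVA, and none of the illustrated Fisher p-values comes near 0.05. All of this stands. It limits the weight of the point, but it does not supply the missing rule for death and discontinuation.

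Three stronger readings are tempting, and the documents do not support them.

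- *A reader might infer that everyone who dies or stops before Week 26 is removed.* That follows only if the Week 26 wording governs. Under the at-least-once wording, a Week 12 or EOT score keeps the subject in.
- *A reader might infer that the rule breaks the randomised comparison in a known direction.* Both arms' rates are inflated. Material distortion of the difference needs unequal loss, and the documents give no loss by arm. In the last row of the table the rule shrinks the apparent benefit.
- *A reader might infer that the trial contradicts itself*, because Protocol 7.3.4.2 plans that subjects "who have an absolute decline of 10 percentage points or more in % predicted FVC or who die will be analyzed using logistic regression". That is a worsening composite with death written into the event, whereas SGRQ response measures improvement on a questionnaire. It shows that counting death as failure was considered for one endpoint. It says nothing about living dropouts, and the SAP's handling of it cannot be checked because SAP 5.2.4 and parts of 5.5 are redacted.

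Nor is every missing score a failure. Incomplete items, remote visits and a delayed Visit 9 also produce missing scores, so the replacement rule must give those subjects a status too.

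**Conclusion.** The concern holds in a limited form. By default the SGRQ responder proportion is an observed-case rate that leaves out subjects who die or discontinue without a qualifying score; how many depends on a time point that the SAP leaves open. Relative to non-responder counting, each arm's rate is overstated by a factor of 1.11 at 10% missing and 1.25 at 20%. With 12 and 6 responders and the plan's 10% overall loss, the difference could move between +5.3 and −12.9 points when the true shift is zero; it does not move when loss is proportional.

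These sizes rest on assumed responder counts and on assumed splits of missing data between arms. Several rows of the table assume more than 10% overall loss, and missing SGRQ need not match the dropout assumed for FVC. The change is worth making before unblinding. It affects one secondary endpoint and leaves the primary FVC analysis untouched.

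**What to change.** In SAP 5.2.3.3:

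1. Define response as a change from baseline in SGRQ total score of −4 or lower at Week 26. Delete the at-least-once qualifier, and reconcile the definition with the all-time-points wording of Protocol 7.3.4.2.
2. Use as denominator all FAS subjects with a baseline SGRQ total score.
3. Count as non-responders subjects who die, or who have no Week 26 score because they discontinued study or treatment.
4. Assign a Visit 9 SGRQ delayed by COVID-19 to Week 26. SAP 3.3.3 already foresees this reassignment in sensitivity analyses of efficacy results, although the detail in SAP 5.2.2.2.4 covers only the primary endpoint. Count any remaining missing score as non-response in the main table.
5. Keep the observed-case proportion as a supportive analysis, with the number missing and the reason shown by arm.

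Cost: a few sentences, one changed denominator in one table and one test, and one supportive table. Both responder rates become somewhat lower, and a few subjects whose score is missing for logistical reasons count as non-responders; the supportive table shows how much that matters.

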4. INTERIM ANALYSES AND DATA MONITORING COMMITTEE REVIEW

4.1. Independent Data Monitoring Committee

To protect the safety of the subjects in the study and integrity of the study data, an IDMC will be implemented. The IDMC will regularly review the accumulating unblinded safety data and assess the benefit risk of the study by further examining pulmonary function per treatment group as evaluated by spirometry and adjudicated clinical endpoints (if available). At each meeting, the IDMC will provide a recommendation to the sponsor on clinical study continuation, suggestions for clinical study adaptation(s) or early termination. No premature study termination is planned for favorable or unfavorable efficacy treatment effect. Specific details on responsibility, composition, meeting formats, and timing are outlined in an IDMC charter. Analysis for the IDMC are detailed in a separate SAP and will be provided to the IDMC by an independent, unblinded statistical support group.

4.2. Interim Analysis

Given the exploratory nature of the study, an interim analysis may be performed in order to allow sponsor planning of following clinical studies. No premature study termination is planned for favorable treatment effect reason based on this potential interim analysis. It is acknowledged that the sponsor may be unblinded by the potential interim analysis. However, all efforts will be made to restrict the access to the study results so that personnel involved with the study conduct remains blinded.

For the interim analysis, a subset of the final analyses will be provided:

- Subject disposition
- Demographics and baseline disease characteristics
- Listings for prior and concomitant therapies and summary table of change in SOC
- Exposure to study medication and compliance
- Primary and selected secondary efficacy assessments:
 - o Change from baseline in FVC (mL)
 - o Change from baseline in 6MWT
 - o Change from baseline in SGRQ total score and domains, and proportion of SGRQ responders
- Listing of adjudicated events
- Safety:
 - o Summary table for treatment-emergent AEs (TEAE) (by stratum)
 - o Frequency tables by system organ class and preferred term for
 - TEAEs (by stratum)
 - TEAEs by severity
 - TEAEs of grade 3/4
 - Serious TEAEs
 - TEAEs related to GLPG1205/placebo
 - TEAEs related to SOC (pirfenidone or nintedanib)
 - o Listings for
 - All AEs (summary)
 - AEs with severity grade 3 or 4
 - SAEs
 - AEs leading to death
 - AEs leading to respiratory-related hospitalization
 - TEAEs leading to discontinuation of GLPG1205/placebo
 - TEAEs leading to temporary stop or dose reduction of GLPG1205/placebo
 - AEs leading to a permanent stop, temporary stop, or dose reduction of SOC

- Descriptive statistics (and figures) of laboratory data, ECG and vital signs
- Frequency tables and shift tables of treatment-emergent laboratory toxicity grades and abnormalities, ECG abnormalities and vital signs abnormalities
- Abnormality listings for laboratory data, ECG, vital signs and physical examination

Outputs will be presented blinded at the IA, with the exception of demographics, baseline disease characteristics, exposure and efficacy output which will be presented unblinded at the group level. Further details of these analyses are provided in Section 5. PK analyses will be covered in a separate analysis plan.

Given there is no plan to terminate the study early for favorable efficacy results, no adjustment of the alpha level is considered needed.

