7.1. DETERMINATION OF SAMPLE SIZE

The aim of this proof-of-concept study is to show a trend in treatment difference for the primary endpoint (change from baseline in FVC over 26 weeks), therefore no formal sample size calculation was performed. In the following paragraph, the variability of the estimated treatment difference for the proposed sample size of 60 subjects is illustrated.

Consider 40 and 20 evaluable subjects in the GLPG1205 and placebo arm, respectively, and an aim of a 50:50 balanced study population being either on nintedanib/pirfenidone or neither. Further, assume for FVC change from baseline at Week 26 a common standard deviation of 200 mL, a true treatment difference of 50 mL in the population receiving nintedanib or pirfenidone and a true treatment difference of 80 mL in the population receiving neither nintedanib nor pirfenidone. Under these assumptions and taking into account 10% dropout, the probability to observe a treatment effect of more than 40 mL in the total study population is 67% and the probability to observe a treatment effect of more than 20 mL is 78%.

Approximately 60 subjects are planned to be randomized into the study.

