7.3.2. Interim Analysis

An unblinded review of data will be performed on a regular basis by an IDMC. See Section 8 for further details. No premature study termination is planned for favorable treatment effect reason. Accordingly, no adjustment of alpha level for testing is performed for this exploratory study.

In addition, given the exploratory nature of the study, an interim analysis may be performed in order to allow sponsor planning of following clinical studies, while maintaining the blind at an individual subject level. There is no plan to terminate the study earlier based on this potential interim analysis. It is acknowledged that the sponsor may be unblinded at the time the interim analysis will take place. However, all efforts will be made to restrict the access to results so that personnel involved with the study conduct remains blinded to the extent possible.

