5.1.1. Demographic and Baseline Disease Characteristics

Summaries will also be provided by stratum (3 levels; nintedanib, pirfenidone, or neither). The following parameters will be considered:

- Date of ICF signature (listed only)
- Sex
- Age at signing the ICF (years)
- Age, categorized (years):
 - $40 \leq \text{age} < 50$
 - $50 \leq \text{age} < 60$
 - $60 \leq \text{age} < 70$
 - $\text{age} \geq 70$
- Race and ethnicity
- Height at baseline (cm)
- Weight at baseline (kg)
- Body mass index (BMI) at baseline (kg/m^2) = $\frac{\text{weight (kg)}}{\text{height}^2 (\text{m}^2)}$
(BMI will not be recalculated if already available in the database)
- BMI, categorized (kg/m^2):
 - $\text{BMI} \leq 18.5$

- $18.5 < \text{BMI} \leq 25.0$
- $25.0 < \text{BMI} \leq 30.0$
- > 30.0
- Baseline systolic and diastolic blood pressure and heart rate
- Baseline alcohol status: no, yes (“Does the patient drink alcohol?”)
- Baseline smoking status: nonsmoker, current smoker, ex-smoker
- Duration of IPF (years) = $\frac{(\text{date of first intake of study drug}) - (\text{date of initial diagnosis})}{365.25}$. If the date of initial diagnosis is incomplete, then the following rules will be applied: Missing day: use the first of the month. Missing month: use January.
- Duration of IPF, categorized (years):
 - duration < 0.5
 - $0.5 \leq \text{duration} < 1$
 - $1 \leq \text{duration} < 2$
 - $2 \leq \text{duration} < 3$
 - duration ≥ 3
- Baseline background SOC:
 - currently taking pirfenidone
 - currently taking nintedanib
 - never took pirfenidone or nintedanib
 - stopped taking pirfenidone and/or nintedanib
- Baseline spirometry:
 - FVC (mL)
 - percent predicted FVC (%)
 - forced expiratory volume in 1 second (FEV₁) (mL)
 - percent predicted FEV₁ (%)
 - FEV₁/FVC ratio
 - forced expiratory flow between 25% and 75% of exhaled volume (FEF₂₅₋₇₅) (mL/s)
- Other baseline efficacy measures:
 - SGRQ total score and domains:
 - symptoms (assessing the frequency and severity of respiratory symptoms),
 - activity (assessing the effects of breathlessness on mobility and physical activity),
 - impact (assessing the psychosocial impact of the disease).
 - 6MWT distance
 - ██████████
- DLCO (corrected for Hb)

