5.1.7.2. Presentation of Results

Summary statistics per treatment group and overall will be provided for each compliance and extent of exposure parameter. Frequency tables will be provided for the compliance parameters, using the following categories: <80%; $80\% \leq x < 100\%$; 100%; $100\% < x \leq 120\%$; > 120%.

A listing will be provided of the subjects who took incorrect study medication (GLPG1205 instead of placebo, or vice versa) for at least part of the treatment period, all GLPG1205/placebo records are to be included to provide an overview of the amount of cross-treatment relative to the total treatment period.

In addition, a listing of the subjects who had their study medication down-titrated or interrupted for at least part of the treatment period will be provided. All GLPG1205/placebo records are to be included to provide an overview of the amount of down-titration/interruption relative to the total treatment period.

Finally, a listing of the subjects receiving investigational product from specific batches, where more than one batch was used (showing the batch numbers of the investigational products actually used, including the expiration dates) will also be provided.

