For each of the spirometry parameters, descriptive statistics will be provided for the actual values, changes and percent change from baseline per time point and per treatment group. Results will also be graphically displayed by means of subject profile plots, boxplots over time by treatment group for the actual values, and line plots of the mean (+/- SE) over time by treatment group for change from baseline, and percent change from baseline.

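### The unblinded interim output keeps minimum and maximum values, and possibly by-stratum tables, so it can compromise the subject-level blind that the protocol requires

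*SAP*

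**What the plan says.** Protocol 7.3.2 permits an interim analysis to help the sponsor plan later studies, "while maintaining the blind at an individual subject level". The same paragraph accepts that the sponsor may become unblinded and promises to restrict access so that people running the study stay blinded as far as possible. SAP 2.7 repeats the promise for study-conduct personnel and sets the individual subject as the minimum level of blinding.

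SAP 4.2 lists the interim outputs as a subset of the final analyses. They are presented blinded, "with the exception of demographics, baseline disease characteristics, exposure and efficacy output which will be presented unblinded at the group level". For details it points to SAP Section 5. There, subject information is summarised with descriptive statistics per treatment group (SAP 5.1). SAP 3.5.2 defines those statistics to include "the median, minimum and maximum". For demographics and baseline disease, SAP 5.1.1 adds: "Summaries will also be provided by stratum (3 levels; nintedanib, pirfenidone, or neither".

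SAP 4.2 does not define group level, does not drop extremes or stratum tables at the interim, and does not say who produces or receives the output. Mock tables and figures are in a separate document (SAP 1).

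**The concern.** In a small trial, the minimum or maximum of a variable within an arm is one subject's actual value. Someone who can see blinded subject-level data can look up whose value it is and so learn that subject's arm. A table can be group-level in form and still give away individual allocations.

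Some of the subject-level data may come in the same package. SAP 4.2 includes abnormality listings for vital signs, presented blinded. SAP 5.3.4.5 says that such listings show the baseline reference time point per subject. Baseline blood pressure and heart rate are also in the SAP 5.1.1 table, which is shown by arm at the interim. For a subject with a listed abnormality, both halves of the match could then be in one delivery.

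Some decisions that depend on blinding may still be open after an interim. Exclusions from the per-protocol set are settled at a blinded data review meeting (SAP 3.1.4), and sensitivity analyses may be added after blinded review (SAP 5.2.2.2). The documents treat individual unblinding as serious: Protocol 4.4.2 withdraws a subject who is unblinded on study, and SAP 3.1.4 removes that subject's efficacy data from the per-protocol set.

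**Working it through.** **Inputs from the documents**
- Size: "Approximately 60 subjects are planned to be randomized into the study" (Protocol 7.1).
- Arms: "Consider 40 and 20 evaluable subjects in the GLPG1205 and placebo arm, respectively" (Protocol 7.1).
- Background: a 50:50 mix of nintedanib/pirfenidone versus neither is the aim (Protocol 7.1).
- Variables: SAP 5.1.1 lists 20 unredacted continuous baseline variables. They are age, height, weight, BMI, two blood pressures, heart rate, IPF duration, six spirometry measures, four SGRQ scores, 6MWT distance and DLCO. The calculation uses at most 18.

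**Assumptions not in the documents**
- Nintedanib and pirfenidone users are equally frequent (25% each).
- There are no ties.
- Correlation between variables is 0 or 0.5.
- Allocation is in permuted blocks of 3 within stratum.
- The interim N is 30 or 60; the plan gives none.
- The reader holds blinded subject-level data including stratum.

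**1. The plan's own figure.** The only design calculation is in Protocol 7.1. The mean difference is 0.5×50 + 0.5×80 = 65 mL. After 10% dropout the arms are 36 and 18, so SE = 200×√(1/36 + 1/18) = 57.7 mL. Then Φ((65−40)/57.7) = 66.7% and Φ((65−20)/57.7) = 78.2%, against 67% and 78% stated. This confirms the arm sizes and mix as read here. It says nothing about blinding.

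**2. Cell sizes at N = 60.** Placebo: 20 × (0.50, 0.25, 0.25) = 10/5/5. GLPG1205: 40 × (0.50, 0.25, 0.25) = 20/10/10.

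**3. Share of subjects who are an extreme on at least one variable.** For k independent variables in a group of n, the share is 1 − ((n−2)/n)^k. With k = 18:
- Arm level: placebo 1 − 0.90^18 = 0.850; GLPG1205 1 − 0.95^18 = 0.603. Weighted: (20×0.850 + 40×0.603)/60 = 0.685. The simulation gives 0.68.
- By stratum: n = 5 gives 1.000, n = 10 gives 0.982, n = 20 gives 0.850. Weighted: (10×1.000 + 30×0.982 + 20×0.850)/60 = 0.94. The simulation gives 0.94.

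With correlation 0.5 the simulated shares fall to 0.50 and 0.83.

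**4. Share whose arm can be deduced.** A subject whose value lies outside one arm's range must be in the other arm, so more subjects can be placed than those who are extremes. Simulation with 300 runs per setting (ranges cover correlation 0 and 0.5):

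| Output | 1 variable | 5 variables | 18 variables |
|---|---|---|---|
| N = 60, arm tables only | 11–12% | 38–45% | 71–89% |
| N = 60, plus by-stratum tables | 32% | 75–81% | 96–99% |
| N = 30, arm tables only | 21–23% | 63–70% | 93–99% |
| N = 30, plus by-stratum tables | 57% | 93–96% | about 100% |

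**5. Effect of removing extremes.** Without minimum, maximum and subject-level plots, this route closes except in stratum cells of one or two subjects. For two values, the mean and SD return both, as mean ± SD/√2. At N = 30 the smallest placebo stratum cell has two subjects or fewer in about 80% of runs. Pooling over strata is therefore needed as well.

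**The case against.** **Subject plots and listings.** A reader might infer that the interim shows individual trajectories and subject listings by arm. The documents do not support this. The spirometry section says "Results will also be graphically displayed by means of subject profile plots, boxplots over time by treatment group for the actual values", where the reference to treatment group may belong only to the boxplots. The exposure section provides "a listing of the subjects receiving investigational product from specific batches", but SAP 4.2 names no exposure listing among its outputs. Read literally, group level excludes both kinds of display.

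**By-stratum tables.** SAP 4.2 attaches a by-stratum tag only to adverse-event tables, which stay blinded. Whether the stratified baseline tables are part of the interim is an inference from the reference to Section 5. This part of the objection stands, so the arm-level figures are the main result.

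**Cell size.** Equal thirds would give about 20/3 = 6.7 placebo subjects per stratum. The planned mix instead points to about 10/5/5.

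**Access.** Nobody learns an allocation from the tables alone; the reader must also hold subject-level data. Both documents promise restricted access, and both accept that the sponsor may be unblinded. This makes the harm conditional. It does not remove the subject-level condition, which Protocol 7.3.2 states in the same paragraph. SAP 4.2 names no recipients and no producing group, although SAP 4.1 has an independent one for the IDMC.

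**Route to bias.** FVC is measured at sites and read centrally, and the decisions to change antifibrotics or stop study drug are the investigator's. Interim recipients would not normally influence these. The plausible exposure is on the sponsor side, in deviation review and analysis choices.

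The minimum/maximum route survives all of this, because extremes by arm are ordinary group-level output.

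**Conclusion.** The point holds in a limited form. SAP 4.2 unblinds four classes of output whose standard displays include extremes, and it drops none of them. That output can compromise the subject-level blind required by Protocol 7.3.2 and SAP 2.7. A reader might go further and say that the interim reveals allocations. The documents do not support that, because matching needs separate subject-level data and access is to be restricted.

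The size depends on how many variables can be matched. At N = 60 with arm-level tables only, it runs from 11–12% of subjects with one variable to 71–89% with 18. If by-stratum tables are included, 18 variables place nearly everyone. These figures assume no ties, so rounding of whole-number variables such as age or heart rate would lower them. An interim on fewer subjects would raise them, but the plan gives no interim size and the analysis is optional. This is a cheap improvement to a stated display rule.

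**What to change.** Amend SAP 4.2 as follows:
- Limit unblinded interim summaries of continuous variables to n, mean, SD or SE, and LS means and differences with 95% CI, by arm and pooled over strata.
- Omit minimum and maximum, and omit by-stratum tables, from the unblinded output.
- State that subject profile plots and subject listings are not shown by arm.
- Have the independent unblinded statistical group already used for the IDMC (SAP 4.1) produce the output, and release it only to recipients with no role in study conduct.

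Removing medians, all boxplots or category counts below 5 is optional and not needed for this point. Any boxplot that is kept should not display the extremes.

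The cost is a short wording change and fewer interim outputs. The sponsor sees less detail at the interim, but the effect estimate and its variability, the main inputs for planning later studies, remain available.
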